### **8.2.5 Study Drug Exposure**

Study drug exposure (in days) for Treatment Period will be calculated as: last dose date of study drug – first dose date of study drug + 1 day, regardless of study drug interruption, and will be summarized descriptively for all parts.

Study drug exposure (in weeks) will be summarized descriptively by the number of subjects (n), mean, SD, median, min, and max. It will also be summarized in categories:  $\leq 2$  weeks,  $>2 - \leq 4$  weeks, and  $>4$  weeks for all parts, using counts and percentages.

Exposure summaries will be based on the Safety Set, and presented by treatment group and overall, for each part. For Part 2, exposure summaries will be based on the Safety Set for the Treatment Period.

### **8.2.6 Study Drug Compliance**

Study drug compliance will be summarized for the Treatment Period only based on the FAS, and will be presented by treatment group and overall.

Study drug compliance will be calculated as:  $100 \times [1 - (\text{total number of days of study drug interruption during the Treatment Period}) / (\text{duration of study drug exposure in days during the Treatment Period})]$ . A study drug interruption on a given day is defined as an interruption of any study drugs on that day.

Study drug compliance will be summarized descriptively by the number of subjects (n), mean, SD, median, min, and max. It will also be summarized in categories:  $<80\%$  and  $\geq 80\%$  using frequency tables.

In addition, percentage of tablets taken will be calculated using the following formula:  $100 \times [(\text{total number of tablets dispensed for the Treatment Period}) - (\text{total number of tablets returned for the Treatment Period})] / (\text{total number of tablets planned to be taken per day} \times \text{duration of study drug exposure in days for the Treatment Period})$ . Summary similar to those for the study drug compliance will be produced based on the FAS.

### **8.2.7 Important Protocol Deviations**

An important protocol deviation (IPD) is a deviation that may significantly affect the completeness, accuracy, or reliability of the study data or that may significantly affect a subject's rights, safety, or well-being. IPD rules will be developed and finalized before completion of Parts 1 and 2.

The protocol deviations that should be considered as potential IPDs include, but are not limited to:

- Subject was enrolled in the study despite the violation of inclusion/exclusion criteria
- Subject was less than 80% compliant with study drug for non-safety reasons
- Subject received prohibited concomitant medications
- Subject received the wrong treatment or incorrect doses
- Subject remained in the study despite meeting withdrawal criteria

Occurrence of any of these events should be considered as potential IPDs, but a blinded team should categorize them as IPDs only if they have the potential to significantly affect the completeness, accuracy, or reliability of the study data or that may significantly affect a subject's rights, safety, or well-being.

IPDs will be provided in an individual subject data listing for each part.

### **8.3 Efficacy Analysis**

All efficacy analyses described in this section will be based on the FAS.

The analysis will include all available measurements through the last scheduled on-treatment visit including measurements after treatment discontinuation, per the visit windowing rules described in [Appendix A](#).

#### **8.3.1 Analysis of the Primary Efficacy Variable**

##### **8.3.1.1 Definition of Variable**

The primary efficacy variable is the absolute change from baseline in percent predicted FEV1 (ppFEV1 in percentage units) through Day 29 in Parts 1, 2, [REDACTED].

The percent predicted FEV1 is the ratio of FEV1 (L) to the predicted FEV1 (L), expressed as a percentage. The predicted FEV1 will be calculated using the Global Lung Function Initiative (GLI); details are in [Appendix C](#).

##### **8.3.1.2 Primary Analysis for Parts 1, 2, [REDACTED]**

The null hypothesis to be tested is that the mean absolute within-group change from baseline in ppFEV1 through Day 29 is zero for VX-121 in triple combination (TC) with TEZ/VX-561 in Parts 1 and 2, [REDACTED] separately. A 2-sided *p*-value of 0.05 or less will be interpreted as sufficient evidence to reject the null hypothesis.

The primary analysis will be performed using a mixed-effects model for repeated measures (MMRM) with change from baseline in ppFEV1 at Day 15 and Day 29 as the dependent variable for each part, separately. The model will include treatment group, visit, and treatment-by-visit interaction as fixed effects and subject as a random effect, with the continuous baseline ppFEV1 as a covariate. For Part 1 the model will include 4 treatment groups: placebo, TC-5 mg, TC-10 mg, TC-20 mg. For Part 2, the model will include 2 treatment groups: placebo + TEZ/IVA, and TC-20 mg. [REDACTED]

[REDACTED] The model will be estimated using restricted maximum likelihood. Denominator degrees of freedom for the F test for fixed effects will be estimated using the Kenward-Roger approximation. An unstructured covariance structure will be used to model the within-subject errors. If the model estimation does not converge, a compound symmetry covariance structure will be used instead.

Conditional on the observed data and covariates, missing ppFEV1 data will be assumed to be missing at random; consequently, no imputation of missing data will be performed.

The adjusted means and 95% confidence intervals (CI) of the average treatment effect through Day 29 (average over Day 15 and Day 29 only) will be presented for all within-treatment and between-treatment comparisons, for each part. A 2-sided *p*-value will be provided for within-treatment comparisons.

Further, the adjusted mean and corresponding 95% CI for each treatment group and the treatment difference between each triple combination and placebo or TEZ/IVA at Day 15 and Day 29 will be provided, for each part. A 2-sided p-value will be provided for within-treatment comparisons.

The adjusted mean (with SE) obtained from the MMRM analysis at Day 15 and Day 29 will be plotted by treatment group, for each part.

In addition, for each part, a descriptive summary of observed values and the changes from baseline in ppFEV1 will be presented for all treatment groups by post-baseline visit through the safety follow-up visit. A waterfall plot showing the subject-level absolute change in ppFEV1 at Day 29 will be presented for each part.

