9.3 Rationale for Study Elements

9.3.1 Study Design

Parts 1 [REDACTED]

Parts 1 [REDACTED] will evaluate the safety, tolerability, PK, PD, and efficacy of VX-121 administered in TC with TEZ/VX-561 (Part 1) [REDACTED] in subjects with CF with F/MF genotypes.

Efficacy has not been established for a corrector, potentiator, or any corrector/potentiator combination in subjects with F/MF genotypes. Because there is no effective treatment for this population, a placebo arm will be included as the control treatment to assess whether any observed effects are treatment-related or simply related to the study conditions.

The Washout Period (18 ± 3 days; Section 9.1.4) is included to enable a more thorough evaluation of VX-121 exposure-response relationships by conducting PK and PD assessments during the VX-121 washout.

Part 2

Part 2 will evaluate the safety, tolerability, PK, PD, and efficacy of VX-121 in TC with TEZ/VX-561 in subjects with CF with the F/F genotype, if the sponsor chooses to conduct this optional part of the study.

The efficacy and safety of TEZ/IVA in F/F subjects have been demonstrated in Study VX14-661-106 (Study 661-106).¹² Therefore, placebo/TEZ/IVA has been chosen as the control treatment to assess whether any observed effects are treatment-related or simply related to the study conditions.

A 4-week TEZ/IVA Run-in Period (Section 9.1.2) is included to establish a reliable on-treatment (TEZ/IVA) baseline for the Treatment Period.

The 4-week Washout Period (Section 9.1.4) is included to evaluate the effect on PD and efficacy endpoints as subjects step down from TC to TEZ/IVA, after the VX-121 washout.

Parts 1, 2, [REDACTED]

The extent of response to CFTR modulator treatment may depend on the subject's ppFEV₁ value (an index of disease severity) before the start of TC study drug dosing. Some subjects in Part 2 (subjects with the F/F genotype) may be receiving treatment with LUM/IVA or TEZ/IVA at screening, while some subjects may not be receiving treatment with CFTR modulators. It is unlikely that subjects enrolling in Parts 1 [REDACTED] (subjects with F/MF genotypes) are receiving LUM/IVA or TEZ/IVA at screening, as the benefit of these drugs has not been established in patients with F/MF genotypes. Therefore, randomization will be stratified by the ppFEV₁ value determined during screening for Parts 1 [REDACTED] and during the TEZ/IVA Run-in Period, after at least 13 days of TEZ/IVA (Day -14 assessment), in Part 2.

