12.3.4 Efficacy Analysis

12.3.4.1 Spirometry

The absolute change from baseline for ppFEV₁ through Day 29 is a primary endpoint in Parts 1, 2, [REDACTED]. The within-group comparisons in the absolute change from baseline for ppFEV₁ through Day 29 will be the primary analysis. A mixed-effects model for repeated measures (MMRM) with change from baseline for ppFEV₁ at Days 15 and 29 as the dependent variable will be performed for the FAS for each part. The null within-group hypothesis of no difference in the mean absolute change from baseline through Day 29 for ppFEV₁, in all treatment groups, by part, will be tested. The model will include treatment group, visit, and treatment-by-visit interaction as fixed effects, subject as random effect and the continuous baseline ppFEV₁ as a covariate. The model will be estimated using restricted maximum likelihood. Denominator degrees of freedom for the *F* test for fixed effects will be estimated using the Kenward-Roger approximation. A compound symmetry covariance structure will be used to model the within-subject errors. Conditional on the fixed effects, missing data due to treatment or study discontinuation will be assumed to be missing at random.

Adjusted means and 95% CIs of the average treatment effects through Day 29 (averaged over Days 15 and 29), as applicable, will be estimated within MMRM using least squares (LS) means via PROC MIXED in SAS, for all within-group comparisons in all parts. *P* values will also be provided for these comparisons. In addition, adjusted means and 95% CIs for the absolute change from baseline for ppFEV₁ through Day 29 will be estimated for between-group comparisons.

For endpoints other than primary, no multiplicity adjustments will be made and the corresponding *P* values for these endpoints will be considered as nominal.

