### Efficacy

The primary efficacy endpoint is the absolute change from baseline in ppFEV1 through Day 29. A sample size of 18 subjects per treatment group provides at least 90% power to detect a mean within-treatment change of 7 percentage points. These calculations assumed a standard deviation of 8 percentage points for the absolute change from baseline in ppFEV1 and were based on EAST, Version 6.4.1.

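### Does a primary ppFEV₁ test of each arm's change against zero need a written rule for reading the difference from control?

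*SAP*

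**What the plan says.** SAP 8.3.1.2 sets the primary test: "The null hypothesis to be tested is that the mean absolute within-group change from baseline in" ppFEV₁ through Day 29 is zero for the TC. A two-sided p-value of 0.05 or less "will be interpreted as sufficient evidence to reject the null hypothesis". Protocol 12.3.4.1 agrees on the ranking: "The within-group comparisons in the absolute change from baseline for ppFEV₁ through Day 29 will be the primary analysis". The protocol applies the null to all treatment groups and the SAP names only the TC, but the SAP gives p-values for within-treatment comparisons generally, so nothing here turns on that difference.

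The comparison with control is also planned. SAP 8.3.1.2 says adjusted means and 95% CIs "will be presented for all within-treatment and between-treatment comparisons, for each part", and asks for TC-minus-control differences at Days 15 and 29. Protocol 12.3.4.1 says adjusted means and 95% CIs "through Day 29 will be estimated for between-group comparisons". P-values are specified for the within-treatment comparisons only.

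Protocol 9.3.1 states why the controls are there. In Part 1, "a placebo arm will be included as the control treatment to assess whether any observed effects are treatment-related or simply related to the study conditions". In Part 2, "placebo/TEZ/IVA has been chosen as the control treatment to assess whether any observed effects are treatment-related or simply related to the study conditions".

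SAP 6.2 gives power for the within-group test alone: 18 subjects per group "provides at least 90% power to detect a mean within-treatment change of 7 percentage points", with SD 8. Protocol 12.1 says the same. SAP 8.3.1.2 is partly redacted and 8.3.1.3 is absent from the public text, so what follows concerns the visible text only.

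**The concern.** Rejecting a null of zero change shows that an arm moved. It does not show that the drug moved it. Any shift shared by all arms adds to the within-group change and cancels in the difference from control. The 5% error rate therefore protects against a false claim of change, not a false claim of difference from control.

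The documents include control arms for exactly this separation, yet the visible text does not connect that purpose to the planned difference and gives no precision for it. With 9 controls the difference will be imprecise. A report could show a clearly significant within-group change beside a difference whose interval covers zero. That pair can arise from a real 7-point effect or from a shared shift, and no reading has been agreed in advance.

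**Working it through.** **Inputs.** SD 8, change 7 and n = 18 come from SAP 6.2. Group sizes are 18, 18, 9 and 9 in Part 1 and 18 and 9 in Part 2 (SAP Figures 6-1 and 6-2). Alpha is 0.05 two-sided. Control change is taken as 0. Dropout and any gain from the baseline covariate are ignored. Model degrees of freedom are 54 − 4 − 1 = 49 (Part 1) and 27 − 2 − 1 = 24 (Part 2).

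**1. The plan's own figure.** The one-sample noncentrality is 7 × √18 / 8 = 3.71. Power is 93.8% with the arm's own 17 df, 94.5% with 24 df and 95.3% with 49 df. The stated minimum of 90% is correct.

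**2. The difference from control.** SE = 8 × √(1/n₁ + 1/n₂); half-width = t × SE.

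| Contrast | SE | 95% half-width | Power at 7 points |
|---|---|---|---|
| 18 vs 9, Part 2 (df 24) | 3.27 | 6.74 | 53.9% |
| 18 vs 9, Part 1 (df 49) | 3.27 | 6.56 | 55.6% |
| 9 vs 9, TC-5 mg (df 49) | 3.77 | 7.58 | 44.4% |
| 9 vs 9, own df 16 | 3.77 | 7.99 | 41.5% |

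**3. How often the two results appear to disagree.** By simulation (1,000,000 trials), with a true effect of 7 and a control change of 0, an 18-subject arm rejects its null while the contrast interval includes zero in 40.2% of trials (Part 1) or 41.0% (Part 2). For TC-5 mg it is about 31%. If SD 8 is per visit, averaging two visits with correlation ρ gives SD = 8 × √((1 + ρ)/2), which is 6.93 at ρ = 0.5 and 7.59 at ρ = 0.8 (assumed values). The 18 vs 9 frequency is then 31 to 38%.

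These figures are close to the gap between the two powers: 95.3 − 55.6 = 39.7 points in Part 1 and 94.5 − 53.9 = 40.6 in Part 2. They restate the contrast's low power and are not a second problem.

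**4. Do the results really conflict?** The chance that the estimated difference is positive is Φ(7 / 3.27) = Φ(2.14), about 98%. Among the apparently discordant trials alone it is still positive in about 97 to 98%, with a median of about 4.6 to 4.7 points. The typical discordant trial shows a positive estimate with a wide interval.

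**5. No drug effect, shared shift.** The documents give no size for a shift. For assumed shifts of 0, 1, 2 and 3 points, an 18-subject arm rejects its null in 5%, 8%, 17 to 18% and 32 to 34% of trials. This is a property of any test against zero, and it is why the planned contrast matters. The contrast keeps its nominal coverage whatever the shared shift.

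**The case for a change.** The strongest case for a change is that the plan invites misreading. It uses the term average treatment effect for within-group means. Protocol 9.3.2 justifies the four-week duration by the separation of active treatment from placebo in earlier studies, which is a between-group argument. Protocol 9.5 aligns Day 1 with the start of an inhaled-antibiotic cycle for subjects who cycle, so a shared shift is plausible. The control arm's own interval (n = 9) is ±5.4 to 6.1 points and would exclude zero in only 10 to 20% of trials at a shift of 2 or 3 points, so inspecting that arm alone is a weak safeguard. Protocol 10.7.1 lets a limited sponsor team use efficacy data for development decisions. A few sentences would cost little.

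What stands is that the visible text does not join the control arms' purpose to the contrast or state its precision. But the natural remedy, a sentence saying attribution rests on the difference and its interval, largely repeats Protocol 9.3.1. Unless it also required the lower limit to exceed zero, it would leave the discordant case unsettled. If it did require that, it would add a test with about 54 to 56% power to a study sized for something else. Neither version improves the estimates the report will contain.

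**Conclusion.** No change is needed. The within-group test is a declared choice for a proof-of-concept study, its power is stated correctly, and the SAP says only that a small p-value rejects a null of zero change. The estimate that addresses attribution is already planned with a 95% interval, from the same model and over the same visits, and the protocol already says what the controls are for. An analyst following the plan would report both results, and a competent reader would judge attribution from the difference.

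The price is imprecision: about ±6.6 to 6.7 points for 18 vs 9 and ±7.6 to 8.0 for 9 vs 9. This can be worked out from the printed SD and group sizes and contradicts no stated figure. It is a fair trade-off at this size. The SAP authors could add a line on the contrast's role and expected half-width as a courtesy to readers, with no protocol amendment.

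These figures assume SD 8 for the subject-level mean change, planned group sizes, no dropout and no gain from baseline adjustment. The shared-shift rates also rest on shift sizes the documents do not give. The conclusion covers the visible text only, given the redactions in and after SAP 8.3.1.2.

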## 11 LIST OF APPENDICES

### Appendix A: Analysis Visit Windows for Safety and Efficacy Assessments

Table 11-1 Analysis Visit Windows for Safety and Efficacy Assessments			
Assessment	Visit	Target Study Day	Analysis Visit Window (in study days)
Part 1			
Serum Chemistry	Day 1 (Baseline)	1	≤1 Pre-dose
Hematology	Day 8	8	[1, 12] Day 1 post dose
Coagulation	Day 15	15	(12, 22]
Weight	Day 29	29	(22, 52]
Standard 12-lead ECG	Safety Follow-up	Not applicable	Use nominal visit
Vital Signs	Day 1 (Baseline)	1	≤1 Pre-dose
Pulse Oximetry	Day 2 (Subjects with Day 2 SP consent)	2	[1, 2] Day 1 post dose
	Day 8 (Subjects with Day 2 SP consent)	8	(2, 12]
	Day 8 (Subjects without Day 2 SP consent)	8	[1, 12] Day 1 post dose
	Day 15	15	(12, 22]
	Day 29	29	(22, 38]
	Day 47	47	(38, 61]
	Safety Follow-up	Not applicable	Use nominal visit
Spirometry (Safety analysis of change from Day 1 to Day 2 in pre-dose ppFEV 1 )	Day 1	1	Use nominal visit
	Day 2	2	Use nominal visit
Spirometry	Day 1 (Baseline)	1	≤1 Pre-dose
	Day 8 (Subjects with Day 2 SP consent)	8	[2, 12] Day 2 post dose
	Day 8 (Subjects without Day 2 SP consent)	8	[1, 12] Day 1 post dose
	Day 15	15	(12, 22]
	Day 29	29	(22, 38]
	Day 47	47	(38, 61]
	Safety Follow-up	Not applicable	Use nominal visit
Sweat Chloride	Day 1 (Baseline)	1	≤1 Pre-dose
	Day 15	15	[1, 22] Day 1 post dose
	Day 29	29	(22, 38]
	Day 47	47	(38, 61]
	Safety Follow-up	Not applicable	Use nominal visit
CFQ-R	Day 1 (Baseline)	1	≤1 Pre-dose
	Day 15	15	[1, 22] Day 1 post dose
	Day 29	29	(22, 61]
Part 2			

Assessment	Visit	Target Study Day	Analysis Visit Window (in study days)
Serum Chemistry Hematology Vital Signs Weight Pulse Oximetry Standard 12-lead ECG	Day 1 (Baseline)	1	≤1 Pre-dose
	Day 8	8	[1, 12] Day 1 post dose
	Day 15	15	(12, 22]
	Day 29	29	(22, 36]
	Day 43	43	(36, 50]
	Day 57	57	(50, 71]
Safety Follow-up	Not applicable	Use nominal visit	
Coagulation	Day 1 (Baseline)	1	≤1 Pre-dose
	Day 8	8	[1, 12] Day 1 post dose
	Day 15	15	(12,22]
	Day 29	29	(22, 57]
	Safety Follow-up	Not applicable	Use nominal visit
Spirometry	Day 1 (Baseline)	1	≤1 Pre-dose
	Day 8	8	[1, 12] Day 1 post dose
	Day 15	15	(12, 22]
	Day 29	29	(22, 36]
	Day 43	43	(36, 50]
	Day 57	57	(50, 71]
Safety Follow-up	Not applicable	Use nominal visit	
Sweat Chloride	Day 1 (Baseline)	1	≤1 Pre-dose
	Day 15	15	[1, 22] Day 1 post dose
	Day 29	29	(22, 36]

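### Subjects whose last spirometry is on or before Day 12 add no outcome data to the primary ppFEV1 model, although Day 8 spirometry is scheduled for everyone

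*SAP*

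**What the plan says.** Both documents restrict the primary model to two visits. SAP 8.3.1.2 uses change in ppFEV1 "at Day 15 and Day 29 as the dependent variable for each part, separately", and protocol 12.3.4.1 has the model "at Days 15 and 29 as the dependent variable will be performed for the FAS for each part". The synopsis names the same two days. The estimate is the average of the Day 15 and Day 29 adjusted means, tested within group against zero, where a two-sided p-"value of 0.05 or less will be interpreted as sufficient evidence to reject the null hypothesis".

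Missing ppFEV1 is taken to be missing at random, "Conditional on the observed data and covariates", with no imputation. SAP 8.3.1.4 plans no sensitivity analysis.

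Protocol Tables 3-1 and 3-2 schedule Day 8 spirometry for all subjects in Parts 1 and 2. SAP Appendix A, Table 11-1, gives Day 8 spirometry its own window, for example in the Part 1 row beginning "Day 8 (Subjects without Day 2 SP consent". That window closes at Day 12. The Day 15 window is (12, 22]. The Day 29 window is (22, 38] in Part 1 and (22, 36] in Part 2. Safety Follow-up is kept as a nominal visit. SAP 8.3 also admits readings taken after treatment discontinuation, assigned by these windows.

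**The concern.** A likelihood-based repeated-measures model can condition only on the outcomes and covariates it contains. If a subject's last reading is on or before Day 12, the subject has no Day 15 or Day 29 value and so contributes no row. The Day 8 response has been observed, but the model does not see it. The missing-at-random assumption for that subject then rests on baseline ppFEV1 and treatment alone, which is more demanding than the SAP's wording suggests.

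The gap can arise in practice. Protocol 9.1.6 asks for the Early Termination of Treatment (ETT) visit as soon as possible after the decision to stop, so a stop around Day 8 can put the ETT spirometry at or before Day 12. The only other scheduled visit is Safety Follow-up, which cannot fill Day 29 because it is kept as a nominal visit.

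The primary test is of a within-group mean against zero. Selective early loss of poor responders in an arm therefore raises that arm's estimate directly, with no control arm to offset it. The planned analyses of the primary endpoint would not measure the effect.

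**Working it through.** **The plan's own figure.** SAP 6.2 gives 18 per group ("A sample size of 18 subjects per treatment group") and says this "provides at least 90% power to detect a mean within-treatment change of 7 percentage points"; on the SD, "These calculations assumed a standard deviation of 8 percentage points". A one-sample t-test with noncentrality 7/(8/√18) = 7/1.89 = 3.71, 17 df and two-sided 0.05 has power 93.8%, so the statement is reproduced. With 17, 16 and 15 contributing subjects the power is 92.3%, 90.5% and 88.3%. An 18-subject group can lose two and still meet the statement. The issue here is bias more than power.

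**Who is affected**, by the spirometry windows:

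- Last reading on or before Day 12: assigned to Day 8 (or baseline), so no row in the model.
- ETT or unscheduled reading on Days 13 to 22: assigned to Day 15, so in the model even if off drug.
- Safety Follow-up reading: nominal visit, so it cannot serve as Day 29.

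**Size of the bias.** From the documents: mean 7 and SD 8. Assumed, because the documents do not give them:

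- a fraction d of 3% to 10% lost before any Day 15 or Day 29 reading;
- a logistic dropout slope of 0.1 to 0.4 per point of Day 8 change, with poorer change making loss more likely;
- the same SD at Day 8, and a slope r of 0.5 to 0.7 for the Day 15/29 average regressed on the Day 8 change (equal to the correlation when SDs are equal).

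Let L be the number of points by which leavers' mean Day 8 change falls below the group mean, found by numerical integration with the intercept set to give d. Stayers then lie above the group mean by S = L × d/(1 − d). The mean without Day 8 is overstated by r × S.

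| d | Slope | L | S | Bias, r = 0.5 | Bias, r = 0.7 |
|---|---|---|---|---|---|
| 3% | 0.1 | 6.06 | 0.19 | 0.09 | 0.13 |
| 3% | 0.4 | 15.48 | 0.48 | 0.24 | 0.34 |
| 5% | 0.1 | 5.87 | 0.31 | 0.15 | 0.22 |
| 5% | 0.4 | 14.18 | 0.75 | 0.37 | 0.52 |
| 10% | 0.1 | 5.42 | 0.60 | 0.30 | 0.42 |
| 10% | 0.4 | 12.17 | 1.35 | 0.68 | 0.95 |

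For example, at d = 10% and slope 0.1, S = 5.42 × 0.10/0.90 = 0.60, and 0.7 × 0.60 = 0.42. As a share of 7 points the range is 0.09/7 = 1.3% to 0.95/7 = 14%. If loss is unrelated to Day 8, L = 0 and the bias is zero.

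**With Day 8 in the model.** A simulation of 4,000 trials per setting used arms of 18, 18, 9 and 9 and a slope of 1.5 per SD (1.5/8 = 0.19 per point). At 10% loss and correlation 0.6 the bias was 0.64 without Day 8 and 0.06 with it, and the SE was 1.94 and 1.97. Over 5% to 15% loss and correlations 0.4 to 0.8, the bias with Day 8 stayed between −0.06 and +0.06. When loss was unrelated to Day 8, both analyses had bias of about 0.01 to 0.02.

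**A harder case.** SAP 8.3 counts readings after discontinuation, so suppose the leavers' true Day 15/29 change is zero (an assumption). With d = 10%, slope 0.1 and r = 0.7, stayers average 7.42 and the true group mean is 0.9 × 7.42 = 6.68. The bias is 7.42 − 6.68 = 0.74 without Day 8 and 7.00 − 6.68 = 0.32 with it. Over the settings in the table, the bias without Day 8 runs from 0.21 to 0.79 and with it from −0.15 to 0.43. It is smaller in absolute size with Day 8 in every setting.

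**The case against.** The strongest reply is that the choice is deliberate and consistent. Both documents prespecify Days 15 and 29, protocol 9.3.2 explains that improvement is seen by Day 15, and a missing-at-random analysis of the endpoint visits is legitimate in a 4-week proof-of-concept study. That stands as a defence of the endpoint. It does not require Day 8 to be left out of the outcome vector, because the estimate can still average only Days 15 and 29.

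The near-zero bias with Day 8 is also partly built in, because the simulation makes dropout depend on the same Day 8 value that the model conditions on. This objection stands. The harder case shows that some bias remains when early stoppers behave differently from subjects who continue.

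The top of the range is extreme. A slope of 0.4 per point is an odds ratio of exp(0.4 × 8) = 24.5 per SD. At 5% to 10% loss, the leavers' Day 8 change would average about −7 to −5 in an arm averaging +7. At slope 0.1 (odds ratio 2.2 per SD) the bias is 0.09 to 0.42, at most 0.42/1.89 = 0.22 of the SE; even 0.95 is about half an SE. At 5% loss, 0.95^18 = 40% of 18-subject arms lose nobody. The calculation also omits the planned baseline covariate.

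Early loss would not be wholly hidden. SAP 8.3.1.2 summarises observed values and changes at each post-baseline visit, and 8.2.1 reports discontinuations with reasons. These displays would show the loss but not its effect on the estimate.

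A reader might infer that everyone who leaves before Day 15 drops out of the primary analysis. The documents do not support this: a reading on Days 13 to 22 counts as Day 15, and subjects without one remain in the Full Analysis Set. Nor would adding Day 8 correct early dropout in general. It addresses only missingness that depends on an observed Day 8 value.

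**Conclusion.** The point holds in limited form. Subjects with no spirometry after Day 12 add no outcome row to the primary model although a Day 8 value may exist, and nothing planned tests the stronger assumption this requires. Under the assumed loss, correlation and slope, the within-group mean is overstated by 0.09 to 0.95 points, roughly 0.1 to 0.9 against the target of 7. The upper end needs a very steep dropout relation. The bias is zero if early loss is unrelated to the Day 8 change or nobody leaves early. This is a minor matter that can be improved cheaply. It does not invalidate the primary analysis, and the documents give no dropout rate from which to say that the bias will occur.

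**What to change.** Add Day 8 as a third outcome visit in the ppFEV1 model, with treatment-by-visit interaction and an unstructured covariance. Keep the primary estimate as the average of the Day 15 and Day 29 least squares means. Endpoint, hypothesis and significance level are unchanged, and no new data or windows are needed.

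A reader might take this for a change to the SAP alone. It is not, because protocol 12.3.4.1 and the synopsis also name Days 15 and 29 and would need to be aligned. If the primary model is to stay as prespecified, put the three-visit model in SAP 8.3.1.4 as the sensitivity analysis.

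The statistical cost is a few more parameters in small groups. The unstructured covariance goes from 2 × 3/2 = 3 to 3 × 4/2 = 6 parameters, and there is one more visit mean per treatment group. The SAP's compound symmetry fallback for non-convergence can remain. The change does nothing for a subject with no Day 8 reading or for missingness driven by values never observed, and the SAP should say so.
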